Study Outcomes: The primary outcome will be the extent to which patients and clinicians engage in SDM during the medical encounter following receipt of the intervention or control. Two secondary outcomes include *Patient quality of decision-making process* (knowledge, decisional confidence, self-efficacy, and satisfaction) and *Preference-congruent decision making* to examine whether patient preferences for or against receiving PSA-based screening align with care received (actual receipt of PSA test, extracted from the electronic medical record).

Subjects: 200 African American men, 40-69 years old, with NO diagnostic of prostate cancer, who are receiving primary care (annual physicals and preventive care) at the clinical sites during the project period (2020-2023).

Intervention: Patients will be randomly assigned to receive a 30-45 minute online educational intervention (n=100) or control group (n=100). Patients receiving the training will learn about prostate cancer (risk, screening, diagnoses and treatment), PSA-based screening (benefits, risks, harms, and guidelines), and SDM process (options, perceptions, preferences, actions). In order to measure the application of the SDM process in the clinical setting (primary outcome), patients will discuss the PSA test with their respective primary care provider (PCPs) during a medical wellness visit (annual checkup). The conversation will be audio-recorded, after patient/PCP's assent, and evaluated to identify the application of the different components of the SDM process. If the audio-recording is not authorized, the patient and PCP will complete an evaluation survey about the encounter. Patients will complete online surveys at enrollment (baseline), during the training (pre-post test), and 3-months after medical encounter (follow-up).

Enrollment: Searches in electronic medical records will be conducted to pre-screen and invite (mail, calls, and emails) eligible patients and their respective PCPs to join the study. Patients will complete in-person or online consent and HIPPA authorizations. PCPs' will complete an online baseline survey and provide implicit consent to join the study.

RESEARCH PROTOCOL

Study Title: Fostering Shared Decision-Making about Prostate Cancer Screening among Clinicians and African American men

1. Study aim, background, and design

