Patients and Primary Care Providers (PCPs) medical encounter (Visit #2): In order to measure the application of the SDM process during the clinical setting, patients will discuss the PSA screening with their respective primary care provider (PCP) during a medical wellness visit (annual checkup). Each week, research team will send a reminder (email and/or phone call) to all enrolled patients having scheduled wellness visits in that week, and their respective Primary Care Providers (PCPs).

This visit may be conducted online or face-to-face, as follow:

Online visit: This wellness visit will take place online. The clinical sites have available telehealth services including Zoom videoconference that are HIPPA compliant. An email to schedule the virtual visit (Appendix 1) will be send by Research team to the respective Patient/PCP. Patients who prefer this option will receive instructions on how to proceed. At the beginning of the meeting, the patient and PCP will confirm that they are in a place where privacy may be preserved and that authorize to audio-record the encounter. If the audio-recording is authorized, the research team member will start the recording. If the audio-recording is not authorized or possible, after the encounter the PCP will rate the conversation using the online evaluation form (Physician-Collaborator Patient Evaluation, Appendix 4) and the-patient will complete the online post-encounter surveys (Intention-to-Screen questions, Shared Decision Making Questionnaire, and Decisional Self-efficacy – Appendix 8B). Once the encounter and evaluations are completed the PCP and patients will receive the respective electronic gift card (\$50 and \$40) for the time spent and any expenses incurred during the visit (transportation, parking, Internet and phone services, etc.).

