Face-to-face visit: This wellness visit will take place in the PCP's consultation room at the respective clinical site and will be audio-recorded after patient/PCP's consent. At the beginning of the encounter the research assistant will ask authorization to record the conversation. If the audio-recording is authorized, the research assistant will start the recording. If the audio-recording is not authorized, the research assistant will bring an evaluation form (Physician-Collaborator Patient Evaluation, Appendix 4) for the PCP to rate the conversation. Once the encounter is completed the research assistant will pick up the recorder or the respective evaluation form and will give the PCP a \$50 electronic gift card as appreciation for the time spent. Immediately after the encounter the patient will complete the post-encounter surveys (Intention-to-Screen questions, Shared Decision Making Questionnaire, and Decisional Self-efficacy – Appendix 8B) and will receive a \$40 electronic gift card as compensation for the time spent and any expenses incurred during the visit (transportation, parking, Internet and phone services, etc.).

Follow-up procedures (Visit #3): At 3-months after the medical encounter (visit #2) patients will complete brief post-intervention surveys (Prostate Cancer Knowledge, Decisional Confidence, Satisfaction with Decision, and Intention-to-Screen questions) and an additional questionnaire about the acceptability of the intervention and procedures. These surveys (Appendix 8C) may be completed online or face-to-face, as follow:

- **Online visit:** Research team will send an email (Appendix 1) to participants including a personalized link to the follow-up surveys including contact information in case that participants have questions.
- **Face-to-face visit:** These surveys will be administrated by the research team in a face-to-face meeting that will be scheduled immediately after the medical encounter (visit #2).

After completing the surveys, patients will receive a \$20 electronic gift card as compensation for the time spent and any expenses incurred during the visit (transportation, parking, Internet and phone services, etc.). Additionally, research team will check each year the medical records of each participating patient to see if they have had or not received a new PSA exam during the study period (Jan 2020-Dec 2023).

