Duration: The entire study procedures for each patient may be completed in around six months, including follow-up (Table 1). It is expected that consent and baseline survey (visit #1) will take about 15 to 30 minutes to fill out. Intervention patients will take around 30-45 minutes completing the educational program, including the pre- and post-tests. The PCP/Patient medical encounter (visit #2) will take around 1 hour according to the clinical site schedules and including time needed for patient to complete the respective surveys. Patients' follow-up assessment (visit #3) will take around 15-20 minutes.

Measures and Outcomes. Outcomes will be assessed using different measures (Appendices 4 and 8) and across different post-intervention intervals: immediately after the clinical encounter (visit #2), and at 3-month (± 15 days; visit #3). The primary outcome will be the extent to which patients and clinicians engage in SDM during the patient-clinician encounter (visit #2) following receipt of the intervention or control, evaluated using the Shared Decision Making Questionnaire (SDM-Q). Two secondary outcomes will include: 1) *patient quality of decision-making process*, assessed at baseline (visit #1), immediately after the patient-clinician encounter (visit #2), and at 3-months post intervention (visit #3) using a composite score of the following scales: Prostate Cancer Knowledge, Decisional Confidence, Decisional Self-efficacy, and Satisfaction with Decision, and 2) *Preference-congruent decision making* to examine whether patient preferences for or against receiving PSA-based screening, assessed with Intention-to-Screen questions at baseline (visit #1) and immediately after the clinical encounter (visit #2) align with care received during the subsequent 3 months (physician orders of PSA screening and actual receipt of PSA screen will be extracted from the electronic medical record). The acceptability of intervention and procedures (Tertiary outcome) will be accessed with a structured questionnaire (Appendix 8) to rate the acceptability of the enrollment process, the delivery of the intervention, and their overall satisfaction with the study that patients will complete at the 3-months follow-up (visit #3). Additionally, patients in the intervention arm will complete an evaluation of the educational intervention and the decision aid questions included in the training (Appendix 8D).

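### The protocol names two different measures for the primary outcome and, as worded, gives online patients the shared decision-making questionnaire only when the visit is not recorded

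*Protocol*

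**What the plan says.** **Synopsis, Intervention.** The encounter is labelled as the place where the primary outcome is measured. The conversation is recorded and evaluated for components of SDM. The survey is a fallback: "If the audio-recording is not authorized, the patient and PCP will complete an evaluation survey about the encounter". The routine survey times that follow do not include the encounter: "Patients will complete online surveys at enrollment (baseline), during the training (pre-post test), and 3-months after medical encounter (follow-up").

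**Section 3, Visit #2, Online visit.** The condition reads "If the audio-recording is not authorized or possible, after the encounter the PCP will rate the conversation using the online evaluation form". In the same sentence the patient "will complete the online post-encounter surveys (Intention-to-Screen questions, Shared Decision Making Questionnaire, and Decisional Self-efficacy"). The next sentence reads more broadly: "Once the encounter and evaluations are completed the PCP and patients will receive the respective electronic gift card".

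**Section 3, Visit #2, Face-to-face visit.** When recording is not authorized, "the research assistant will bring an evaluation form (Physician-Collaborator Patient Evaluation, Appendix 4) for the PCP to rate the conversation". The patient forms carry no such condition: "Immediately after the encounter the patient will complete the post-encounter surveys".

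**Section 3, Duration.** Visit #2 is timed at about an hour, "including time needed for patient to complete the respective surveys", again without condition.

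**Section 3, Measures and Outcomes.** The primary outcome is evaluated with the SDM-Q, and the recording is not mentioned. Both secondary outcomes draw on an assessment immediately after the encounter.

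**Table 1, Visit #2.** It lists Shared Decision Making-Patient, Shared Decision Making-PCP, Intention-to-Screen and Decisional Self-efficacy, all unconditionally. No audio rating appears.

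**Section 4, Risks.** Encounters are recorded so that SDM can be rated, the rating is done by research personnel, and the audio is deleted six months after Visit #2.

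**The concern.** There are two problems, and the first is the more serious.

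**Which measure is primary.** An observer's rating of a recorded conversation and a questionnaire filled in afterwards by a participant are different measures, with different raters. The synopsis points to the first and Measures and Outcomes to the second. Under the synopsis, the kind of measure a patient has also depends on whether recording was authorized at the visit, which is decided after randomisation.

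**Who completes the patient forms.** If the SDM-Q is primary and staff follow the online-visit wording, a recorded online patient has no primary outcome value. The same sentence would withhold two forms used for the secondary outcomes:

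- Decisional Self-efficacy is a component of the decision-quality composite. After baseline it is scheduled only at Visit #2; the Visit #3 lists in Section 3 and Table 1 omit it.
- The Visit #2 Intention-to-Screen answer is one of the two readings on which preference-congruence is defined.

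A form not given right after the encounter cannot be supplied later by any analysis plan. A late decision in favour of the audio rating could find the recordings already deleted.

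**Working it through.** The protocol gives no figure on this point to reproduce, so the check is mainly a comparison of texts.

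| Place | Measure of SDM at Visit #2 | Patient forms | PCP form |
|---|---|---|---|
| Synopsis, Intervention | Evaluated recording | Only if recording refused | Only if recording refused |
| Section 3, Online visit | – | In the sentence conditional on no recording | Only if no recording |
| Section 3, Face-to-face visit | – | Every patient | Only if recording refused |
| Section 3, Measures and Outcomes | SDM-Q | Visit #2, no condition | Not mentioned |
| Table 1, Visit #2 | Patient and PCP SDM measures; no audio rating | No condition | No condition |
| Section 4, Risks | Recording rated by research staff; not called primary | – | – |

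The first column of content conflicts between the synopsis and Measures and Outcomes/Table 1. The patient-form column conflicts between the online text (and synopsis) and the face-to-face text and Table 1. The PCP column conflicts with Table 1 only if the Appendix 4 evaluation is the Shared Decision Making-PCP measure. Appendix 4 is not shown, so that part stays open.

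**Illustrative counts.** Inputs: 200 patients, 100 per arm (protocol). Let *o* be the share of encounters held online and *r* the share recorded. The protocol gives neither; the values below are assumptions, taken as equal in both arms and with *r* the same online as face to face.

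*Reading A: SDM-Q primary, forms given to all.* Patients lacking the SDM-Q: 0 of 200.

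*Reading B: SDM-Q primary, online wording followed literally.* Number lacking it = 200 × *o* × *r*, from 0 to 200. With a fraction *f* = *o* × *r* lost in each arm, the standard error of the arm difference grows by √[100 / (100(1 − *f*))] = 1/√(1 − *f*).

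| *o* | *r* | *f* | Lacking SDM-Q | SE factor |
|---|---|---|---|---|
| 0.25 | 0.70 | 0.175 | 35 | 1/√0.825 = 1.10 |
| 0.50 | 0.80 | 0.400 | 80 | 1/√0.600 = 1.29 |
| 0.75 | 0.90 | 0.675 | 135 | 1/√0.325 = 1.75 |

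*Reading C: synopsis governs.* Patients with a survey in place of a rating = 200 × (1 − *r*): 60 at *r* = 0.70, 40 at 0.80, 20 at 0.90.

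No effect size, significance level or power enters these figures.

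**The case against.** The strongest reply is that the operative definition has a clear home. Measures and Outcomes is the only text that names an instrument for the primary outcome, Table 1 fits it, and the conflicting text is a synopsis paragraph about the intervention. The Risks section says recordings are rated but does not call the rating primary, so it could be an additional measure whose role an analysis plan (not available here) would describe. This narrows the conflict without removing it: the synopsis expressly attaches the primary outcome to the recorded encounter and makes the survey a fallback, and nothing says which text prevails.

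On the online wording, the reply is that it is a drafting slip. The payment sentence, the visit duration, the face-to-face text and Table 1 all suggest surveys for everyone, and the online option was added in Version 2. That is likely right, and it makes data loss a risk rather than an expectation. But the synopsis uses the same fallback logic and leaves the encounter out of its list of routine survey times, so staff following those two texts would find them consistent.

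Two smaller points stand. Intention-to-Screen is also asked at baseline and Visit #3, so only its Visit #2 reading would be lost. And because the counts run from 0 to 200 on assumed shares, they show a range of possibilities and estimate nothing.

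**Conclusion.** The concern holds. The protocol gives two incompatible answers to what the primary outcome is, and its online-visit wording, taken literally, withholds the patient's Visit #2 questionnaires whenever the visit is recorded. This goes beyond detail that an analysis plan could supply, because it determines which data are collected.

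Confidence is high on the contradiction itself, which rests on the text alone. The data loss depends on staff following the online wording as written and, for the primary outcome, on the SDM-Q being the intended measure. Its size is unknown: none if forms are given to all, up to every patient in the extreme, with the assumed shares above giving 35 to 135 of 200. No bias between arms is claimed. The PCP form is a question for the authors.

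**What to change.** 1. Name one primary measure and use it consistently in the synopsis, Measures and Outcomes and Table 1. The SDM-Q is the natural choice: it is already named and can be collected from every patient whether or not recording is allowed. If the audio rating is intended instead, Measures and Outcomes and Table 1 must be corrected to say so.
2. State the role of the audio rating in the synopsis, Measures and Outcomes and the Risks section. Do not let the rating and the questionnaire stand in for each other.
3. Reword the synopsis and the online-visit text so that the patient SDM-Q, Intention-to-Screen and Decisional Self-efficacy forms are completed after every encounter, whatever the visit mode or recording status, as the face-to-face text already provides. The last two forms are needed for the secondary outcomes whichever primary measure is chosen.
4. Say whether Table 1's Shared Decision Making-PCP is the Appendix 4 evaluation. If it is, make that form unconditional in both visit modes or correct Table 1.

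The cost is protocol wording and an IRB amendment, the existing patient forms after recorded online visits as well, and possibly one short PCP form per recorded encounter. No new instrument or extra visit is needed.

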Below is the **Study Design Schema** about the randomization of patients and assessment for both the intervention and the control arms (Figure 1) and the **schedule of activities** and measures to be completed (Table 1).

Figure 1: Study Design Schema

[figure not shown]

Table 1: Study activities and measures to be completed

Visit	Timeline	Procedure	Outcome	Measures
-------	----------	-----------	---------	----------

Visit #1 Consent & Baseline (15-60 min)	After initial contact with patient	Review/sign consent and HIPPA forms		
 • Consent form • HIPPA authorization form
		Complete baseline assessment	Secondary outcome: Patient quality of SDM	
 • Prostate Cancer Knowledge • Decisional Confidence • Satisfaction with Decision • Decisional Self-efficacy
			Secondary outcome: Preference-Congruent DM	
 • Intention-to-Screen questions • PSA screening orders and actual receipt of PSA screen, extracted from the electronic medical record
Intervention (30-45 min)	Before visit #2	Patients in intervention arm: complete training		
 • Prostate Cancer Knowledge • Intention-to-Screen questions • Decision aid questions • Evaluation of training
Visit #2 Medical encounter (approx. 1 hour)	During 3 months after visit #1 and intervention	Complete medical encounter	Primary outcome: Patient and clinicians engagement in SDM	
 • Shared Decision Making-Patient • Shared Decision Making-PCP • Intention-to-Screen questions • Decisional Self-efficacy
Visit #3 Follow-up (15-20 min)	3 months after visit #2	Complete follow-up assessment	Secondary outcome: Patient quality of DM	
 • Prostate Cancer Knowledge • Decisional Confidence • Satisfaction with Decision
			Secondary outcome: Preference-Congruent DM	
 • Intention-to-Screen questions • PSA screening orders and actual receipt of PSA screen, extracted from the electronic medical record
			Tertiary outcome: Acceptability of intervention and procedures	
 • Acceptability of Intervention • Intervention Appropriateness • Feasibility of Intervention

4. Risks

The risks to the patients as participants are minimal.

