All patients will be asked information regarding their self-identified race/ethnicity, as well as cancer screening (i.e. having or not a prostate exam). The discomfort anticipated with some of these questions is similar to that experienced when completing a form in the doctor's office.

Patients in the intervention arm will receive information regarding prostate cancer and risks and may suffer discomfort and feel embarrassed because of some images included in the training, such as the ones showing the prostate location in the human body (Appendix 9, page 2). However, it is expected that any adult patient having routine clinical visits may be exposed to similar images at any time during their lives.

Although patients will have been physically and mentally prepared for the clinical encounter, it is possible that they will suffer discomfort and feel embarrassed because of the clinical encounter. It is not possible to avoid these risks and patients will be clearly informed about them. However, these are the common risks

experienced by any person having routine clinical visits and it is expected that any man may face these decisions at any time during their lives.

The research does not have any impact on the rights and welfare of participants. No personal information (name, address, phone, emails) will be kept about invited patients refusing to join the study. However, those refusing to participate in the study will be asked reasons for no participation. Aggregated data about those refusing to participate will be reported in the study procedures and manuscripts. On the other hand, patients completing the project activities will receive training and monetary compensation for the time spent and any cost incurred for their participation.

There is minimal risk of loss of privacy. There is the potential for loss of confidentiality: 1) Participants' personal information (name, phone, email and address) will be collected and used to contact them along the study timeline. 2) Patients medical records will be examined to find history of PSA screenings, and 3) the clinical encounters will be audio-recorded to rate the application of the shared-decision making (SDM) during the clinical encounter. Although appropriate efforts will be made to protect the privacy of patients' identifiable information, any accidental disclosure would not place participants at risk or harm.

Procedures to minimize identified risks:

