Participants considering the interventions offensive, risky, embarrassing, or not appropriated to their cultural beliefs, may stop participating at any time. No additional information about these participants will be collected when they stop participating.

Codes will be assigned to each patient participating so it is possible to match pre-tests and post-tests with real performance during the clinical encounters but at the same time protect patients' privacy. Codes will be assigned by research personnel once the consent form is signed (visit #1) and will be recorded, instead of names, in all study records (surveys, medical encounter, intervention, etc.). Names, address, email and phone numbers will be used by research team only to contact the participants. Qualtrics, the software to capture and store project data, uses Transport Layer Security (TLS) encryption for all transmitted Internet data and has the functionality to ensure the confidentiality of survey results. Microsoft OneDrive, which uses encryption for files (at-rest and in-transit), was approved by Xavier Office of Technology Administration to share project files among the research team.

The patient informed consent process includes authorization to audio-record the clinical encounter and the HIPAA authorization to access health records. Only contact information (name, address, phones and email) and PSA screenings (having or not PSA screening) will be extracted (entered to a digital file) from the medical records and patient will be identified with the respective code assigned. Only authorized research personnel (listed in the IRB application) will have access to the medical records. Audio recording of the clinical encounter, where PSA screening is discussed, will be rated by research personnel. Audio files will be password protected, kept in secured computers for 6 months after the medical encounter (visit #2), and then deleted. No copies of these audios will be made. However, clinicians participating in the medical encounter may write a note into the respective patient health record about the decision of ordering or not the PSA test as part of the decision making process.

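### The primary outcome is measured in different ways in different sections, and as written no single score is collected from every man

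*Protocol*

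**What the plan says.** The protocol describes how the primary outcome is measured in several places.

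- **Synopsis, Study Outcomes.** Gives the construct and no instrument: "The primary outcome will be the extent to which patients and clinicians engage in SDM during the medical encounter following receipt of the intervention or" (the last word, naming the comparator, is left out here).
- **Synopsis, Intervention.** Attaches the primary-outcome label to the visit conversation: "In order to measure the application of the SDM process in the clinical setting (primary outcome), patients will discuss the PSA test". It continues: "The conversation will be audio-recorded, after patient/PCP's assent, and evaluated to identify the application of the different components of the SDM process". Surveys enter only as a stand-in: "If the audio-recording is not authorized, the patient and PCP will complete an evaluation survey about the encounter".
- **Section 4, Risks.** Says that "the clinical encounters will be audio-recorded to rate the application of the shared-decision making (SDM) during the clinical encounter", and under the procedures to minimize risks: "Audio recording of the clinical encounter, where PSA screening is discussed, will be rated by research personnel". No rating scale is named.
- **Section 3, Measures and Outcomes.** The same outcome is "evaluated using the Shared Decision Making Questionnaire (SDM-Q"), with no respondent stated and no mention of the recording.
- **Section 3, Table 1, Visit #2.** Lists "Shared Decision Making-Patient" and a matching PCP form under the primary outcome, and no audio rating.
- **Section 3, Visit #2 procedures.** For online visits, the PCP form and the patient's post-encounter surveys (including the SDM questionnaire) are both written as conditional on there being no recording. For face-to-face visits, only the PCP form is conditional; the patient completes the surveys in any case. Permission to record is asked at the start of either kind of visit.
- **Section 1.** Names generalized linear mixed models for the SDM hypothesis but not the dependent variable.

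**The concern.** An observer's rating of a recording, a patient's self-rating and a clinician's rating are three different measurements of one encounter. They need not share a scale, a mean or a variance, so one cannot replace another for individual men. The protocol presents all three in connection with the primary outcome and neither ranks nor combines them.

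Two things are at stake. First, if an analyst completes the primary dataset by taking whichever score exists, the source of a man's score is fixed by recording status. Permission is asked again at Visit #2, after training, when a man in the intervention arm knows he was trained. Any difference between arms in recording then enters the treatment comparison. Second, if several scores are available and none is named, the primary conclusion can rest on whichever turns out favourable.

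**Working it through.** **1. What each place makes the primary measure**

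| Place | Audio rating | Patient form | PCP form |
|---|---|---|---|
| Synopsis, Intervention | main measure | stand-in if not recorded | stand-in if not recorded |
| Section 3, Measures and Outcomes | not mentioned | SDM-Q, respondent not stated | SDM-Q, respondent not stated |
| Table 1, Visit #2 | not listed | listed | listed |

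The construct agrees throughout. The instrument and the rater do not.

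**2. What the visit procedures collect, read literally**

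This takes the PCP evaluation form in Appendix 4 (not shown) to be the PCP form of Table 1.

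| Visit #2 | Audio rating | Patient SDM-Q | PCP form |
|---|---|---|---|
| Online, recorded | yes | no | no |
| Online, not recorded | no | yes | yes |
| Face to face, recorded | yes | yes | no |
| Face to face, not recorded | no | yes | yes |

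No column reads yes in all four rows. The patient SDM-Q comes closest and fails only for recorded online visits.

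**3. Size of the problem if scores were pooled (illustration)**

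The only input from the protocol is 100 men per arm. It states no alpha, power, effect size or SD, so its sample size cannot be reproduced and is not in dispute here. Assumed: two-sided alpha 0.05, within-source SD of 1, no true effect, a mean gap g between score sources, and recorded shares r1 and r0 in the two arms.

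- Bias = (r1 − r0) × g
- Variance in each arm = 1 + g² × r × (1 − r)
- SE = sqrt[(v1 + v0) / 100]
- Type I error = 1 − Φ(1.96 − bias/SE) + Φ(−1.96 − bias/SE)

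Worked case, g = 1.0, shares 80% and 60%: bias = 0.20 × 1.0 = 0.20 SD; v1 = 1.16, v0 = 1.24; SE = sqrt(2.40/100) = 0.155; type I error 25.2%.

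| Gap g (SD) | Shares | Bias (SD) | Type I error |
|---|---|---|---|
| 0.5 | 70% vs 60% | 0.05 | 6.4% |
| 0.5 | 80% vs 60% | 0.10 | 10.6% |
| 1.0 | 70% vs 60% | 0.10 | 9.8% |
| 1.0 | 80% vs 60% | 0.20 | 25.2% |

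For scale, the difference detectable with 80% power on one clean score is (1.960 + 0.842) × sqrt(2/100) = 0.40 SD, so the largest bias shown is half of it. With equal shares of 70% there is no bias, but power at 0.4 SD falls from 80.7% to 78.7% (g = 0.5) or 73.0% (g = 1.0).

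**4. Size of the problem if the score were chosen freely**

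For independent tests at 5%, the chance of at least one false positive is 1 − 0.95² = 9.75% for two scores and 1 − 0.95³ = 14.3% for three. With equally correlated test statistics (simulation, 1,000,000 draws):

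| Correlation | Two scores | Three scores |
|---|---|---|
| 0.5 | 9.1% | 12.5% |
| 0.7 | 8.4% | 10.9% |
| 0.9 | 7.0% | 8.4% |

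**The case against.** The best defence is that the protocol already has a primary measure. The Measures and Outcomes paragraph is the fullest statement and names the SDM-Q. Table 1 agrees in listing questionnaires only. The recording sentence stands in a synopsis paragraph about the intervention, so the recording could be extra process data. Scoring and combining the two forms is commonly left to the SAP, which is not at hand. This has weight: it shows which measure the text favours. It does not settle the matter. The synopsis attaches the primary-outcome label to the recorded conversation, the SDM-Q sentence names no respondent while Table 1 gives two, and the online procedure, as written, does not collect the SDM-Q when there is a recording. An SAP cannot recover a form that was not completed.

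Stronger readings are tempting, and the protocol does not support them:

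- *That scores from different raters will be pooled.* No section says so. The text only leaves it open, and the bias figures are conditional on it.
- *That patient and PCP both decide on recording knowing the arm.* A trained man knows he was trained, but nothing says that the PCP is told the arm.
- *That permission is first sought after training.* Patient consent at Visit #1 already includes authorization to record (Sections 3, 4 and 10). Refusal at Visit #2 remains possible because both visit procedures ask again.
- *That the type I error could reach 29%.* That follows from SE = sqrt(2/100) = 0.141, which ignores the variance added by mixing two score levels. With it, the same case gives 25%.

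**Conclusion.** The concern holds as an inconsistency in the protocol's own text, with an operational consequence: followed literally, the procedures leave the primary outcome without any one score available from all men, and what is available depends on recording status and visit mode. This is more than detail deferred to an SAP, and it should be fixed before the primary analysis is specified.

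How much harm results cannot be known from the document. Pooling would give a bias of 0.05 to 0.20 SD and a type I error of about 6% to 25%, under the assumed gaps and recording shares. A free choice would give about 7% to 10% with two scores and 8% to 14% with three, at an assumed alpha of 0.05 and depending on correlation. These are illustrations of what the wording permits, not forecasts. A reader might infer that the trial plans to mix raters or to pick among scores; it states neither.

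**What to change.** - **Name one primary score**, with respondent, instrument and time point. The patient SDM-Q at Visit #2 is closest to the Measures and Outcomes paragraph and is already collected from every face-to-face patient.
- **Collect it from everyone.** Amend the online procedure in Section 3 so that the patient completes the SDM-Q whatever the recording status. Changing only the outcome definitions would leave recorded online visits without a primary score.
- **Delete the substitution rule** in the synopsis, and make the synopsis, both Visit #2 procedures, Measures and Outcomes, Table 1 and the recording text in Section 4 agree.
- **Keep the audio rating and the PCP form as separate supportive outcomes**, never merged with the primary or used in its place.
- **Optional:** turn the existing consent authorization into a recorded yes/no choice before randomisation, and ask PCPs for standing permission in the Background Survey, both still revocable at the visit.

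The cost is mainly wording, plus one short patient survey at recorded online visits and, if the option is taken, one item each in the consent and the PCP survey. There is a real downside: the primary becomes a self-report by men who are not blind to their training, and it covers only the patient's side of a construct that includes clinicians. The audio and PCP results must therefore be shown beside it. If the sponsor prefers another single measure, the same requirements apply: one score, one respondent or rater, obtained from every man.
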